1 PROTOCOL SYNOPSIS

PROTOCOL TITLE	A Multicenter, Randomized, Double-Blind, Placebo-Controlled Ascending Dose Study to Evaluate the Safety, Tolerability, PK and PD Effects of Posiphen® in Subjects with Early AD
PROJECT DIRECTORS	[name]. and [name].
COORDINATING CENTER	Alzheimer's Disease Cooperative Study (ADCS)
STUDY DESIGN	
A Phase 1b multicenter, randomized, double-blind, placebo-controlled study evaluating safety, tolerability, PK and PD of 23-25 days exposure to multiple ascending doses of Posiphen in up to 24 participants with a clinical profile consistent with early AD including Mild Cognitive Impairment due to AD (MCI-AD) or Mild AD with the following planned doses:
 
 • 60 mg Once a Day (QD) (1x60mg) • 60 mg Twice a Day (BID) (2x60mg) • 60 mg Three Times a Day (TID) (3x60mg) 
Each dose group will include 8 subjects, 5 randomly assigned to Posiphen and 3 randomly assigned to placebo.
 
Each dose group will be completed and evaluated for safety and tolerability by the standing ADCS Data Safety Monitoring Board (DSMB). The ADCS DSMB will determine whether to approve dose escalation.
 
Subjects who do not tolerate study drug during the initial 3-week at-home treatment period will be discontinued and replaced by new subjects. If two subjects at a given dose are discontinued due to adverse events, no additional subjects will be added at this dose level until a safety review has been conducted. The safety committee will determine the appropriate dose level for additional subjects. The safety committee has the option to change the allocation of future patients to active drug versus placebo based on statistical advice to maintain an appropriate balance between placebo subjects and subjects on active drug.

DURATION OF STUDY PARTICIPATION	Each subject will have up to a 42-day screening period, followed by approximately 21-23 days of treatment at home, and an in-clinic visit that includes treatment and a 36-hour lumbar puncture (LP) Stable Isotope Labeling and Kinetics (SILK™) procedure.
SUMMARY OF INVESTIGATIONAL PRODUCT	Posiphen 60 mg QD, 60 mg BID or 60 mg TID, or placebo capsules taken orally for up to 25 days.

SUMMARY OF KEY ELIGIBILITY CRITERIA	
• Clinical profile consistent with early AD including MCI-AD or mild AD according to the core clinical criteria outlined in the National Institute Aging (NIA) and Alzheimer's Association (NIA-AA) Guidelines• Cerebrospinal fluid (CSF) AD biomarkers consistent with AD (Beta Amyloid 42(Aβ42)/Beta Amyloid 40(Aβ40) ratio less than 0.131 as measured by mass spectrometry)• Age 55-89 (inclusive), in good health with no frailty• Mini-Mental State Examination (MMSE) score between 17 – 30 (inclusive) -• Clinical Dementia Rating (CDR) global score of 0.5 with a memory score of 0.5 or greater, or global score of 1.0
PRIMARY OUTCOME MEASURE	Aim 1. Safety and Tolerability Aim 2. PK of Posiphen/metabolites in Plasma and CSF Aim 3. PD on fractional synthesis rate (FSR) of Beta Amyloid 40 (A β 40) in CSF
OTHER KEY OUTCOME MEASURES / STUDY PROCEDURES	Aim 4. Feasibility of SILK™ in a multicenter trial Aim 5. PD on other biomarkers in CSF including Beta Amyloid 38 (A β 38), A β 40, A β 42, Soluble Amyloid Precursor Protein alpha (sAPP α), Soluble Amyloid Precursor Protein alpha (sAPP β), and T-Tau Aim 6. Cognitive and/or neuropsychiatric effects of Posiphen

2 INTRODUCTION

The medications that are currently approved for AD target symptoms such as memory loss, but the magnitude of the effect is small, and the clinical benefits are limited. Aducanumab (commercially known as Aduhelm™), an A β -directed monoclonal antibody, received accelerated approval by the FDA for the treatment of early AD in June 2021.

Posiphen® is a selective inhibitor of amyloid precursor protein (APP) production and has potential utility as a disease modifying treatment for AD (Cullen 2006; Utsuki 2006; Lahiri 2007). Posiphen was discovered at the National Institute on Aging and was selected from a series of structurally related compounds designed for APP specificity with no minimal or minimal acetylcholinesterase inhibitory activity. Posiphen was shown to reduce APP and consequently beta-amyloid (A β) production in relevant preclinical in vitro and in vivo studies.

Posiphen, developed by Annovis Bio, Inc., is a small molecule that is thought to act by lowering soluble APP protein levels through a post-transcriptional mechanism. Iron increases the translation of APP by binding to an iron-responsive element (IRE) that forms a stem loop structure in the 5' untranslated region (5'UTR) of APP Messenger Ribonucleic Acid (mRNA). Iron regulatory proteins bind to these stem loop structures and suppress the iron activation of mRNA translation. Iron Regulatory Protein 1 (IRP1) selectively binds the APP IRE with an affinity of 35 pM. When IRP1 is bound to the stem loop, it prevents the complex from binding to the ribosome and prevents translation of the mRNA. Addition of Posiphen to human derived cell line (SH-SY-5Y) neuroblastoma cells increases the affinity of IRP1 to the stem loop structure to 15 pM and lowers the rate of translation of the mRNA by the ribosome (Venti 2004; Cahill 2009; Cho 2010; Rogers 2011). A study conducted to analyze the effect of orally administered Posiphen on A β levels in the mouse brain, revealed that Posiphen lowered A β levels at plasma concentrations that are attainable with oral dosing in humans (IB 2015). Three Phase 1 studies have been completed with Posiphen. The first study was a single ascending dose (SAD) study in healthy volunteers; the second study was a multiple ascending dose (MAD) study in healthy volunteers, and the third study was one with a PK/PD study of biomarkers in CSF obtained from mild cognitively impaired participants.

The present study will confirm the pharmacokinetics of Posiphen and its metabolites in plasma and CSF. More importantly, it will expand on the biomarker reduction seen in the mechanism of action study (Maccecchini 2012) by measuring the effects of a 23-25 day treatment period with Posiphen on the CSF and plasma levels of a number of biomarkers, inflammatory factors and control proteins. It will also expand the safety data in humans by extending the treatment period from 10 days to a treatment period from 23-25 days. In addition, this study will measure concentrations of various soluble biomarkers in CSF and use the SILK™ assay methods to directly measure the effect of Posiphen on the fractional synthesis rate of A β 40 in CSF, which will help guide the further development of Posiphen and determine the feasibility of SILK™ in a multicenter trial.

2.1 Primary Aims

Aim 1: To determine the safety and tolerability of multiple ascending doses of Posiphen on subjects with early AD with up to 23-25 days of daily usage.

Aim 2: To determine the PK of Posiphen and its metabolites in plasma and CSF of subjects with early AD treated with QD, BID and TID dosing regimens.

Aim 3: To assess the PD effects on the FSR of A β 40 using the SILK™ technique with multiple doses of Posiphen.

2.2 Secondary Aims

Aim 4: To implement a multicenter lumbar CSF catheter study employing standardized methodology and SILK™ technology. The following criteria will be evaluated as outcomes to determine feasibility:

- Enrollment comparisons of research subjects at each of the 3 sites
- Adequacy of sample collections to permit analyses of PK and PD effects of Posiphen
- Subject satisfaction questionnaires
- Comparison of protocol deviations and variances in data between the sites

Aim 5: To assess the PD effects of treatment with Posiphen versus placebo on the levels of the following biomarkers in CSF of subjects with early AD:

- A β 38 and 40
- sAPP α
- sAPP β
- T-tau protein (T)

Aim 6: To assess whether there are short-term cognitive and/or neuropsychiatric effects of Posiphen in subjects with early AD, either positive or negative.

- ADAS-Cog12
- MMSE
- Neuropsychiatric Inventory (NPI)

3 PRELIMINARY STUDIES

The following is a brief summary of the available information on Posiphen. Detailed information can be found in the Posiphen Clinical Investigational Brochure (2015).

3.1 Summary of Non-Clinical Findings

In wild type mice, Posiphen lowered brain APP and A β levels by up to 60% ([Lahiri 2007](#), [Cullen 2006](#)). In APP transgenic AD mice, Posiphen led to a decrease in APP levels, improved neuronal stem cell survival and increased levels of brain-derived neurotrophic factor (BDNF) ([Marutle 2007](#); [Kadir 2008](#), [Lilja 2013](#)). Chronic administration of Posiphen to APP transgenic mice totally prevented decline in memory and learning at plasma concentrations that are easily attainable with oral dosing in humans ([Maccecchini, Sambamurti & Arancio in preparation](#)). In

alpha-synuclein (aSYN) transgenic PD mice, Posiphen restored gut motility to normal ([Maccecchini, Kuo & Nussbaum in preparation](#)).

Posiphen was not mutagenic or clastogenic as assessed by in vitro assays.

The cardiac electrophysiological properties of Posiphen tartrate were negative in vitro using human ether-a-go-go related gene (hERG) transfected human embryonic kidney cells (HEK 293). Posiphen did not adversely affect the interval seen in an electrocardiogram (ECG) test (QT (or QTc)) interval.

Toxicity studies in dogs showed brain toxicity (ataxia and tremors/twitching) and gastrointestinal (GI) toxicity at 30 mg/kg/day, which was dose-dependent and reversible. The no observed adverse effect level (NOAEL) was 20 mg/kg/day in dogs. Posiphen readily crosses the blood-brain barrier. The signs/symptoms noted at high doses of Posiphen may be related to cholinergic manifestations. In in vitro assays, Posiphen showed minimal inhibition of AChE or BChE (Butyrylcholinesterase) activity, however, a metabolic product of Posiphen, N1-norposiphen demonstrated acetyl cholinesterase inhibitory activity (Yu 2013). There were no effects on the reproductive organs associated with 4-week exposure to Posiphen in male or female rats or dogs.

3.2 Summary of Clinical Findings

Three Phase 1 studies have been conducted with Posiphen (Annovis Bio, Inc. 2019). The first was an SAD study in healthy volunteers; the second was an MAD study in healthy volunteers, and the third one was a PK/PD study of CSF obtained from mild cognitively impaired participants.

In the multiple ascending dose trial, Posiphen was administered orally in doses of 20, 40, and 60 mg 4 times a day (QID). The first two treatments were administered for 7 days, and the third, for 10 days. Single doses were given on the first and last day to determine the pharmacokinetics of the drug. In general, the drug was well tolerated, resulting in no serious or severe adverse events and only one premature discontinuation, a subject in the 60 mg group discharged because of nausea, vomiting, dizziness and “feeling warm.” The incidence of adverse events, all of either mild or moderate severity also occurred with similar frequency in the placebo group. The most common AEs were dizziness, headache, and nausea/vomiting.

Posiphen was absorbed rapidly after oral administration, achieving maximum plasma and CSF concentration (C_{max}) within 1.2 - 1.5 hours. For the 40 and 60 mg doses, with fully defined plasma profiles, the mean terminal $t_{1/2}$'s were 3.80 ± 0.88 and 5.23 ± 1.24 hours, respectively after a single dose and 3.53 ± 1.03 and 4.104 ± 0.91 hours, respectively, after repeat dosing. The half-life ($t_{1/2}$) of the plasma concentrations at the lower doses could not be calculated accurately. The C_{max} increased disproportionately with dose (24, 144, and 2310 ng.h/mL after a single dose of 20, 40, and 60 mg, respectively and 110, 134, and 2101 ng.h/mL after multiple doses of 20, 40, and 60 mg, respectively).

In the proof of mechanism of action study, the PK of Posiphen was measured after 10 days of administration (4x60 mg) over 12 hours in CSF and plasma of the AD participants. The PD of a number of biomarkers was compared for 12 hours before the first dose at day 0 and after the last dose at day 11 of Posiphen administration. We found that the plasma concentrations of Posiphen overlapped with the plasma concentrations found in the MAD study. In this study, the N1 metabolite reached about 10 to 15%, while the level of the N8 metabolite reached about 20 to 25% of the Posiphen levels measured in plasma.

Because a substantial proportion of the adverse events observed in AD participants treated with cholinesterase inhibitors appear to reflect the cholinomimetic properties of molecules in this

class, Posiphen's highest tolerated dose is determined by the levels of the N1-norposiphen in blood and brain.

While the $t_{1/2}$ of Posiphen in plasma was 5 hours as seen in the SAD and MAD studies, the $t_{1/2}$ in CSF/brain was longer than 12 hours. Concentrations of Posiphen in the brain, extrapolated from blood and CSF, were 8 times higher than in plasma. 10 days of treatment with Posiphen normalized CSF levels of Soluble Amyloid Precursor Protein (sAPP) and tau, reduced α SYN and a series of inflammatory markers. The concentration and persistence of Posiphen in the brain suggest that much lower doses of drug administered once daily could achieve the desired pharmacological effect.

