Dose selection: Posiphen will be tested at doses of 60 mg QID, 60 mg BID (120 mg total daily), and at 60 mg TID (180 mg total daily). Whereas the plasma t $\frac{1}{2}$ of Posiphen has been determined to be 5 hours, the CNS t $\frac{1}{2}$ is estimated to be over 12 hours, allowing that once daily dosing may be feasible. However, previous studies indicated that likely cholinergic adverse events are mostly driven by Cmax. In particular, in the SAD study significant nausea, vomiting and dizziness occurred at a single dose of 160mg. In the MAD study 40mg QD (=160 mg/day) was well tolerated. Thus, the same total daily dose is better tolerated if divided into several doses. The use of multiple doses compared to once a day in this study will help evaluate the PK/PD relationship in the context of tolerability of different administration schemes.

Study Design: This study is designed as a Phase 1b multicenter, randomized, double-blind, placebo-controlled study evaluating safety, tolerability, PK and PD of 23-25 days exposure to multiple ascending doses of Posiphen in up to 24 participants with a clinical profile consistent with early AD including MCI-AD or Mild AD with the following planned doses:

- 60 mg QD (1x60mg)
- 60 mg BID (2x60mg)
- 60 mg TID (3x60mg)

Each dose group will include 8 subjects, 5 randomly assigned to Posiphen and 3 randomly assigned to placebo.

There is some risk of excess cholinergic adverse events given that some subjects will be included who are on cholinesterase inhibitor treatment for Alzheimer's disease which may become additive with the first metabolite of Posiphen (N1-norPosiphen) that has anticholinesterase properties.

Therefore, each dose group will be completed and evaluated for safety and tolerability by the standing ADCS DSMB before the next dose group is initiated.

Subjects who do not tolerate study drug during the initial 3-week at home treatment period will be discontinued and replaced by new subjects. If two subjects at a given dose are discontinued due to adverse events, no additional subjects will be added at this dose level until a safety review has been conducted. The safety committee will determine the appropriate dose level for additional subjects. The safety committee has the option to change the allocation of future patients to active drug versus placebo based on statistical advice to maintain an appropriate balance between placebo subjects and subjects on active drug.

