9.5.2 Confinement Visit

The confinement visit will last just over 2 days and will consist of four phases: admission, 36-hour sampling, 12-hour observation, and discharge. Subjects will be provided with meals (note: some restrictions are specified below) and sleeping accommodations during this visit. For a complete list of all visit procedures, refer to the Schedule of Events (Appendix 1) and to the Confinement Visit Diagram (Appendix 3).

Phase 1: Admission

Subjects should arrive fasted in the early morning after an overnight fast. Clinical safety labs will be drawn and sent to the local lab for analysis.

Study drug compliance over the preceding days will be assessed. If there is an insufficient level of drug compliance (less than 80% overall and or less than 80% in the last week), the site must consult with the Project Directors and Medical Monitor regarding timing and conduct of the remaining confinement visit procedures. It is possible that subjects will be discontinued early from the study due to insufficient study drug compliance.

Admission visit procedures include conducting a brief Physical and Neurological Exam, collecting vital signs, reviewing and recording adverse events and concurrent medications. Please refer to Appendix 3.1, Confinement Visit Phase 1: Admission Diagram.

Phase 2: 36-Hour Sampling

For an overview of the 36-Hour Sampling time points, please refer to the Confinement Visit Schedule of Events (Appendix 3.2b).

If no medical or compliance concerns are identified during the admission procedures, the subject will move on to the 36-Hour Sampling Phase, which entails the following procedures:

1. Place an intravenous line (for infusion) as well as a second venous line for blood sampling
2. Place the CSF catheter
3. Collect initial samples of blood and CSF

4. Administer assigned study drug (will vary based on blinded treatment assignments) at 0 hours
5. Begin the $^{13}\text{C}_6$ -labeled “heavy” leucine infusion. Subjects will receive an initial bolus of 3 mg/kg over 10 minutes, followed by 8 hours and 50 minutes of continuous intravenous infusion at a rate of 2 mg/kg/hour. The total leucine administration with the bolus is 9 hours
6. Provide a low leucine meal (NOTE: all food provided during the heavy leucine infusion must conform to low leucine dietary guidelines; refer to Appendix 4, Sample Low Leucine Menu and to the Procedures Manual for more details)
7. Continue with the following for 36 hours:

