 - a. Collect CSF (6 mL) and blood (10mL) every 2 hours at the following time points: 0, 2, 4, 6, 8, 10, 12, 14, 16, 18, 20, 22, 24, 26, 28, 30, 32, 34 and 36 hours; all collection times should be calculated from the start of the heavy leucine infusion. Samples should be in separate tubes and sent to the ADCS Biomarker Core
NOTE: If unable to obtain a total of 6 mL CSF at any given collection time (e.g., due to participant headache or participant’s CSF production level) please obtain the maximum amount possible and notify ADCS Clinical Operations
 - b. At 0 hours, an additional 1-2 ml CSF (or volume per Local laboratory requirements) should be sent ambient to the local laboratory for protein, glucose, and cell counts
 - c. Perform safety monitoring every 4 hours while the subject is awake. This includes questions about any symptoms in relation to the CSF catheter (including potential adverse events such as leg or back pain, dizziness or headaches) and vital sign monitoring. Participants also should be asked about pain, redness or swelling at the IV site in the arm
 - d. Administer assigned study drug (will vary based on blinded treatment assignments) every 8 hours – at 8, 16, 24, and 32 hours
 - e. Provide low leucine meals and snacks as needed during the duration of the heavy leucine infusion; return to normal diet after completion of the infusion (Refer to Appendix 4, Sample Low Leucine Menu)
 - f. Subjects remain at bedrest throughout the CSF sampling period of 36 hours. They are allowed to use a bedside commode for toileting
8. 36 hours after the start of the heavy leucine infusion, collect the final blood and CSF samples. An extra 9mL of whole blood should be sent to the central lab for the metabolic panel and a CBC/Diff. An extra 2mL of CSF should be sent to the local lab for protein, glucose, and cell counts
9. Remove the blood and LP catheters
10. Perform final safety monitoring, a brief physical and a brief Neurological Exam

If the subject experiences intolerable AE(s) that require early discontinuation of the sampling procedures and removal of the LP catheter, contact the Medical Monitor and Project Directors as soon as possible to discuss the situation. If feasible, the standard 12-hour observation and discharge procedures should be followed to allow for management and follow-up on the adverse events.

Phase 3: 12-Hour Observation

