5.1 Primary Aims

5.1.1 Aim 1

To determine the safety and tolerability of multiple ascending doses of Posiphen on subjects with early AD with up to 23-25 days of daily usage. Safety and tolerability will be summarized using the following tables, listing and figures:

- Vital signs
- Adverse events onset before randomization
- Adverse events onset after randomization
- AE overall
- AE by severity
- MedDRA coded AEs
- Percentage of AEs summarized by SOC
- Number of participants with at least one AE
- Number of AEs summarized by System Organ Class (SOC) and Preferred Terms (PT)
- Serious AEs (SAE) onset after randomization
- Death summary
- Hospitalization summary
- Safety Labs

5.1.2 Aim 2

To determine the PK of Posiphen and its metabolites in plasma and CSF of subjects with early AD treated with QD, BID and TID dosing regimens., samples will be analyzed at baseline time 0 pre first dose then at times 2H, 4H, 8H, 12 H, 16H, 20H and 24H post dose. Further doses are provided every 8 hours. Curves and area under the curve will be constructed for each of the three sequential dose cohorts of 60 mg daily, 60 mg BID, and 60 mg TID.

Standard PK parameters will be calculated for each subject, including AUC, C_{max} , t_{max} , $t_{1/2}$, V_{ss} . Dose-proportionality will be assessed on C_{max} and AUC statistics. Plasma concentrations will be displayed with time series plots including individual and means by dose. PK parameters summarized descriptively (N,

[figure not shown]
mean (SD) and 95% CI, median, min, max, and geometric mean (%CV) as appropriate) by each dose regimen. Accumulation ratio will be determined. CSF levels will be evaluated by dose levels and correlated where possible to blood levels.

The Charles River Lab in Montreal will analyze PK of Posiphen and its metabolites in Plasma and CSF. This will include Posiphen, N1-Desmethyl Posiphen (Phenserine) and N8-Desmethyl Posiphen (Phenserine). Phenserine is an enantiomer of Posiphen. The chromatographic assay used does not distinguish between the two enantiomers, so these metabolites represent the total amount of both.

5.1.3 Aim 3

To assess the PD effects on the FSR of Ab 40 using the SILK™ technique with multiple doses of Posiphen.

The schema for evaluating the Fractional Synthesis and Clearance Rate, the Absolute Synthesis and Clearance and Area under the concentration curve are presented in **Figure 1**.

The analytic techniques to calculate these values are undertaken by C2N.

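### With no blood draw in the first 2 h after any dose, plasma tmax cannot confirm the reported 1.2-1.5 h and plasma Cmax is modestly understated

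*Protocol*

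**What the plan says.** - **Expected peak.** Protocol 3.2 says oral Posiphen is absorbed quickly, "achieving maximum plasma and CSF concentration (C_{max}) within 1.2 - 1.5 hours".
- **Half-life.** The same section gives plasma half-lives for 40 and 60 mg of "3.80 ± 0.88 and 5.23 ± 1.24 hours, respectively after a single dose" and "3.53 ± 1.03 and 4.104 ± 0.91 hours, respectively, after repeat dosing". The half-life "in CSF/brain was longer than 12 hours".
- **Dosing and draws.** Protocol 9.5.2 takes the initial blood and CSF first, then has staff "Administer assigned study drug (will vary based on blinded treatment assignments) at 0 hours", with further capsules at 8, 16, 24 and 32 h. Blood and CSF are collected "every 2 hours at the following time points: 0, 2, 4, 6, 8" and so on to 36 h. Protocol 12.2.3 repeats this grid for plasma.
- **Assays.** SAP 5.1.2 analyses the pre-dose sample, "then at times 2H, 4H, 8H, 12 H, 16H, 20H and 24H post dose".
- **Outputs.** Protocol 6.4 and SAP 5.1.2 list Cmax and tmax among the PK parameters. Protocol 6.4 adds a geometric mean and between-subject CV for each, tmax included. Cmax also enters dose-proportionality and, in SAP 5.2.2, a PK/PD regression.
- **Why Cmax is of interest.** The dose-selection paragraph of Protocol 4 states that "likely cholinergic adverse events are mostly driven by Cmax".

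**The concern.** PK in plasma and CSF is a primary aim, and Protocol 2 says the study will confirm Posiphen's pharmacokinetics. A maximum taken from timed samples can be no earlier and no higher than the samples allow. If the peak lies at 1.2-1.5 h and sampling starts at 2 h, the recorded plasma tmax is set by the draw schedule. A report of 2 h would look like slower absorption than in the earlier studies when only the grid has changed. The planned CV for tmax would say almost nothing about subjects.

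The recorded plasma Cmax is read on the falling limb. It is therefore low, most of all in fast absorbers, whose early peak is missed by the widest margin.

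**Working it through.** The documents state no figure that this point needs to reproduce. The check compares the grid with the doses, then sizes the loss with a simple model.

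**1. Grid against doses**

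| Capsule (clock h) | First protocol draw after it | First SAP assay after it |
|---|---|---|
| 0 | 2 h (2 h post-dose) | 2 h (2 h post-dose) |
| 8 | 10 h (2 h post-dose) | 12 h (4 h post-dose) |
| 16 | 18 h (2 h post-dose) | 20 h (4 h post-dose) |
| 24 | 26 h (2 h post-dose) | none listed |
| 32 | 34 h (2 h post-dose) | none listed |

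No draw falls between 0 and 2 h after any capsule. Protocol 6.4 bases calculations on actual sampling times, but that adds no earlier sample.

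**2. Model**

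One compartment with first-order absorption:
- C(t) is proportional to exp(-ke·t) - exp(-ka·t).
- ke = ln 2 / half-life.
- ka is solved from tmax = ln(ka/ke)/(ka - ke).

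Inputs from Protocol 3.2 are tmax 1.2 and 1.5 h, plasma half-life 3.53 to 5.23 h, and CSF half-life set at 12 h, the lower limit given.

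Worked extremes for plasma, single dose:
- Half-life 3.53 h, tmax 1.2 h: ke = 0.1964, ka = 2.216; C(2)/C(1.2) = 0.6633/0.7201 = 0.921.
- Half-life 5.23 h, tmax 1.5 h: ke = 0.1325, ka = 1.912; C(2)/C(1.5) = 0.7453/0.7629 = 0.977.

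Ratio C(2 h)/Cmax for tmax 1.2 h / 1.5 h:

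| Half-life | Single dose | QD steady state | TID steady state |
|---|---|---|---|
| 3.53 h | 0.921 / 0.971 | 0.921 / 0.970 | 0.904 / 0.952 |
| 4.104 h | 0.929 / 0.973 | 0.928 / 0.972 | 0.911 / 0.953 |
| 5.23 h | 0.941 / 0.977 | 0.939 / 0.975 | 0.922 / 0.956 |
| 12 h (CSF) | 0.970 / 0.987 | 0.965 / 0.983 | 0.954 / 0.969 |

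The typical loss is about 2-10% in plasma and 1-5% in CSF. A two-compartment plasma profile gives ratios of 0.87-0.97, a loss of 3-13%. A dose first sampled at 4 h shows 62-77% of its plasma peak.

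**3. Recorded tmax**

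The 4 h sample exceeds the 2 h sample only if the true tmax is above about 2.8-2.9 h. The documents give no between-subject spread for tmax, so a range is assumed:
- Mean tmax 1.35 h, CV 30-50%, half-life 4.10 (SD 0.91) h, no assay error: plasma tmax reads 2 h in 97-99.7% of subjects. Mean Cmax loss is 6-8%, and the worst 5% lose at least 16-21%.
- Mean tmax 1.2-1.5 h, CV 30-60%: mean Cmax loss is 5-12%, and the 5th-percentile subject loses 13-26%. Plasma tmax reads 2 h in 94% to essentially all subjects without assay error, and in 89-98% with 10% error.
- CSF with 10% error on the SAP grid: tmax reads 2 h in only 55-79%.

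With five active subjects per dose group, the chance that all five read 2 h in plasma, even with assay error, is 0.89^5 = 0.56 to 0.98^5 = 0.90. The planned CV would then be zero.

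**4. Between-regimen comparison**

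The TID/QD ratio of sampled Cmax is multiplied by 0.904/0.921 = 0.982 at one extreme and 0.956/0.975 = 0.981 at the other, a shift of about 2%.

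**5. Effect of early draws**

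With samples at 1, 1.5 and 2 h, the highest sampled plasma level is 99-100% of the modelled peak at steady-state QD and TID. The recorded tmax is then 1 or 1.5 h.

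**The case against.** The strongest reply is that the loss is small against the trial's precision. If Cmax has a between-subject CV of 20-50% (an assumption; none is given), the 95% half-width for a mean of five is 2.776 × CV/√5, about 25-62%. A bias of a few percent is lost in that. Protocol 6.4 also calls the PK preliminary and determines parameters as the data permit. The main PK/PD predictor in SAP 5.2.2 is the trough, which is unaffected. All of this stands for mean Cmax. None of it helps tmax, because no sample exists that could show a value near 1.2-1.5 h.

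The inputs are also uncertain. The earlier studies' sampling and meal conditions are not described, and Protocol 9.5.2 gives a meal after the time-0 dose. A later peak would shrink the Cmax loss. Protocol 7.2 gives the lower-dose groups a mix of active and placebo capsules without saying which slot is active, so an active capsule at time 0 is assumed. If it falls at 8 or 16 h, the first SAP assay comes 4 h after it and the loss is larger.

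A reader might infer that safety is compromised because the protocol names Cmax as the driver of cholinergic events. The documents do not carry that. The Cmax sentence is used to support dividing the daily dose. Protocol 3.2 ties the highest tolerated dose to N1-norposiphen, whose tmax is not given, so no bias can be computed for it. No analysis of Cmax against adverse events is planned, and escalation rests on DSMB review of safety and tolerability.

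**Conclusion.** The point holds, most firmly for plasma tmax. As sampled, it cannot read below about 2 h (leaving aside a chance pre-dose maximum). It will read 2 h in roughly 89-99.7% of active subjects under the assumed spread and 0-10% assay error. The trial therefore cannot confirm or refute the earlier 1.2-1.5 h.

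Plasma Cmax is biased low, but modestly: about 2-10% in a typical subject, and about 13-26% or more in the most affected 5%. The first range rests on the protocol's own tmax and half-lives in a one-compartment model. The second also needs the assumed between-subject spread.

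It would be wrong to infer a gross understatement, or one that applies equally to CSF or dose-proportionality. CSF loses about 1-5% and its tmax is less tied to 2 h. A similar fractional loss in each regimen largely cancels. The change is worth making because it is cheap and concerns a primary aim.

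**What to change.** In Protocol 9.5.2 and 12.2.3, add plasma-only PK draws at 1 h and 1.5 h after the time-0 dose, taken from the venous sampling line already placed, with no extra CSF. Add both times to the assay list in SAP 5.1.2. The cost is two small draws and two assays per subject. Dosing and the SILK sampling grid are untouched.

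If sampling is already complete, change the wording of Protocol 6.4 and SAP 5.1.2 only. Do not summarise observed tmax as an estimate of time to peak or compare it with 1.2-1.5 h. Report Cmax as the highest sampled concentration, state that the first post-dose sample was at 2 h, and call it a lower bound on the true peak.

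Two other remedies are weaker. Renaming the value as a 2 h concentration would mislabel any maximum that falls later. A model-estimated Cmax would depend on an absorption rate that is poorly identified without early samples.
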